7.3.2 Clinical Laboratory Evaluations

All laboratory results will be listed by treatment, subject, and visit, including scheduled and unscheduled measurements. Laboratory assessments that are outside of normal ranges will be flagged.

Baseline values, the values at each visit, and changes from baseline values will be summarized for each of the quantitative laboratory assessments by treatment.

Shift tables of laboratory results will be used to summarize changes from Baseline to the end of the Follow-up Visit (V15) or Early Termination/Withdrawal.

Laboratory data collected during Screening will be summarized descriptively.

7.3.3 Vital Signs and Physical Examinations

Vital signs at Baseline (Visit 3), each scheduled visit, and changes from baseline at each visit will be summarized and listed. Physical examination findings will be listed only.

[figure not shown]
7.3.4 Daily Diary Card

Subject diaries are a source for the Investigator to identify potential adverse events experienced by the subject during the study with the severity of any findings. All signs and symptoms of associated with the warts after randomized study medication injections, as recorded in the daily diary cards, will be summarized by the most severe grading from each subject, and will be provided in listings. Since Diary Card events are recorded by subjects, analysis will not be summarized in the Final Report, but all adverse events will be.

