3.2 Secondary Endpoints

1. Incidence of site injection AE for all subjects and TEAE for subjects randomized to CANDIN

Protocol Final version 5.0: 06Dec2016

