9.7.1.2 Local Reactions

The following reactions occurring within 7 days following the injection of Investigational Product, as judged by the Investigator based upon the subject diary entries, discussion with subject, and the scale in Protocol Section 9.2.2, also judged by Investigator as possibly, probably, or definitely related to the Study Drug:

[figure not shown]
- Pain (Severity Grade 4)
- Tenderness (Severity Grade 4)
- Erythema/Redness (Severity Grade 4)
- Induration/Swelling (Severity Grades 3-4)

[figure not shown]
If a subject fails to contact the Investigator about the occurrence of a severity Grade 4 local reaction, the Investigator and Medical and Safety Monitor will investigate this event to characterize the severity and grade of the event, before recommending the stopping of the subject.

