2.2 Secondary Objectives

Secondary objectives include the following:

1. To assess the safety and tolerability of Candin.

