4.2 Secondary Endpoints

Secondary endpoints include the following:

1. Assessment of safety and tolerability of Candin:

Incidences of DTH Challenge immediate reactions and immediate injection hypersensitivity/reactions after study treatment, and all other treatment-emergent adverse events.

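### SAP 7.3.4 plans a worst-grade summary of diary-recorded local reactions and then keeps it out of the Final Report, so diary reactions not recorded as adverse events would reach no summary table

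*SAP*

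**What the plan says.** SAP 7.3.4 (Daily Diary Card) makes three statements in one short paragraph.

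- It gives the diary a role: "Subject diaries are a source for the Investigator to identify potential adverse events".
- It plans an analysis. Wart-related signs and symptoms recorded after injections "will be summarized by the most severe grading from each subject, and will be provided in listings".
- It then restricts reporting, on the ground that subjects make the entries: "analysis will not be summarized in the Final Report, but all adverse events will be".

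The secondary objective in SAP 2.2 is "To assess the safety and tolerability of Candin". The matching endpoint in Protocol 3.2 is "Incidence of site injection AE for all subjects and TEAE for subjects randomized to CANDIN". In SAP 4.2 it is "Incidences of DTH Challenge immediate reactions and immediate injection hypersensitivity/reactions after study treatment, and all other treatment-emergent adverse events". Neither endpoint names the diary.

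The diary is used elsewhere. Under Protocol 9.7.1.2 the investigator judges local reactions for individual stopping "based upon the subject diary entries, discussion with subject, and the scale in Protocol Section 9.2.2". SAP 7.2.4 includes diary data in the medical assessment of the first eight Cohort 2 subjects, before Cohort 3 opens. It also includes them in the assessment of the first five subjects of Cohorts 2 and 3, which governs the pace of inclusion.

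**The concern.** Two consecutive sentences plan a table and then bar it from the report, and nothing says where it will appear. A programmer could not tell from 7.3.4 whether it is a deliverable.

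The only reason given is that subjects make the entries. That is a reason to label the table. It does not justify leaving it out, particularly when the plan uses the same entries in safety decisions during the trial.

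At stake is one view of local tolerability. The trial compares 0.3 mL in one wart, 0.5 mL in one wart, and 0.3 mL per wart in up to four warts at a visit. A reader of the report would want to see, by group, how severe the local reactions were as subjects recorded them. Without the diary table, the report shows only those reactions that were recorded as adverse events, at the severity the investigator assigned.

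**Working it through.** No arithmetic applies. The documents give no expected rate of diary reactions and no share of them that becomes adverse events. The check is a comparison of sections.

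1. **Is the summary planned?** Yes. SAP 7.3.4 specifies the statistic (worst grade per subject) and listings. SAP 7.1 says data summaries are in general presented by treatment group: pooled placebo and the three CANDIN cohorts. The planned table is therefore a four-group table.

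2. **Is it reported?** No. The last sentence of SAP 7.3.4 excludes it from the Final Report and names no other destination. The listings would still hold the individual entries, but a listing gives no group rates.

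3. **Does an endpoint lose its analysis?** No. The endpoints in Protocol 3.2 and SAP 4.2 rest on adverse events and immediate reactions. Protocol 14.5.2.1 and SAP 7.3.1 summarise TEAEs, including by severity, and treat injection-site TEAEs separately. SAP 7.3.4 itself keeps all adverse events in the report.

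4. **Do the adverse-event tables necessarily contain every diary reaction?** The public text does not establish this.
   - Protocol 9.2 names diaries and visits as two possible sources of injection-site adverse events, in permissive wording. It gives causality and severity to the investigator.
   - SAP 7.3.4 calls the diary a source of potential adverse events only.
   - The local-reaction scale in Protocol 9.2.2 starts erythema and induration at 2.5 cm, so a smaller reaction has no size grade on it. The visible text does not say whether such a reaction is recorded as an adverse event.
   - Protocol 9.2 does require that all adverse events in randomized subjects go into the source documents and eCRF. That binds once something counts as an adverse event. It does not say which diary entries count.

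5. **Is the stated reason consistent with the rest of the plan?** Only weakly. Protocol 9.7.1.2 and SAP 7.2.4 both rely on diary entries, together with medical judgement, for decisions about subjects and cohorts.

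6. **Are the data there?** Yes. Protocol Appendix A and SAP Table 1 have the diary handed out at every injection visit (V3 to V12) and reviewed from V4 to V13.

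Points 2 and 4 together give the result: a diary reaction that is not recorded as an adverse event would appear in no summary table of the Final Report.

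**The case against.** The strongest defence is that the paragraph is a coherent choice. The diary is an input to medical judgement. The investigator reviews it, talks to the subject, grades the reaction on a common scale and records an adverse event. Reporting the assessed events and leaving the raw entries to listings fits that role. The worst-grade summary could be meant for the medical reviews alone. The permissive wording in Protocol 9.2 can also be read as naming two sources, with no licence to discard entries. The public protocol text runs from section 7.1 to 7.8 and lacks 9.1 and 9.5, so a rule for converting diary reactions may stand there.

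Much of this stands. The two sentences can be reconciled, but the SAP does not say that this is what it means. The absence of a visible conversion rule cannot be charged to the plan as a proven gap. The exclusion, however, is stated outright, and its reason sits badly with the use made of the diaries elsewhere.

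A reader might also infer more than the documents support:

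- **That the secondary objective loses its data.** It does not. Its endpoints are based on adverse events and stay fully reported.
- **That the diary is the only information collected systematically.** Appendix A schedules adverse-event review at every visit, scarring and hypopigmentation assessment from V3 to V15, and 30 minutes of observation after each injection.
- **That reported adverse events are a subset of diary entries.** Protocol 9.2 lets injection-site events arise at visits too, so either source can hold events that the other lacks.
- **That the difference between groups would be understated by a known amount.** No rate in the documents supports such a figure. Investigators are blinded, so the documents give no reason for recording to differ by arm.

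**Conclusion.** The point holds in a limited form. SAP 7.3.4 withholds an already planned tolerability table from the Final Report for a reason that the rest of the plan does not bear out. The loss is the subject-reported worst-grade table by treatment group, and with it any summary of diary reactions that were not recorded as adverse events. The analyses of the secondary endpoints are untouched.

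The size cannot be computed. If every diary reaction is recorded as an adverse event, the report loses only the subjects' own grading. If some are not, those reactions are missing from its summary tables. The documents do not say where between these cases the trial would fall. The conclusion assumes that no conversion rule stands in the unseen protocol sections. If one does, the second part of the loss shrinks or disappears, but the inconsistency within 7.3.4 remains. This is a worthwhile improvement to reporting and does not threaten the trial's main conclusions.

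**What to change.** Replace the last sentence of SAP 7.3.4 with a statement along these lines: the worst-grade diary summary will be presented by treatment group in the Final Report, labelled subject-reported, beside the injection-site TEAE table, and all adverse events will also be summarized. Replacing the sentence is better than deleting it, because it also carries the commitment to report adverse events.

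The cost is one extra table in the report, from a summary that the SAP already plans. The downside is that diary and adverse-event counts will differ. A footnote should explain why: subjects record the diary entries, the investigator assesses the adverse events, and adverse events may also be identified at visits.

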8 CHANGES TO THE PLANNED ANALYSES

9 SAMPLE SIZE AND POWER

10 STATISTICAL SOFTWARE

All analyses will be performed with SAS® version 9.4.
